Demonstration in a pilot, single-center trial of the usefulness of real-time, repeated hand-held spirometry to provide objective measurements of lung function in AECOPD will have a substantial impact on both patient health outcomes and on health care utilization and will set the stage for appropriate next-step studies and NIH grant applications. It is unknown whether this specific technology will be acceptable in our population, though previous research suggests that older patients may be willing to use home monitoring technology. Our multi-disciplinary team includes providers from the Department of Medicine and the UCM COPD Readmissions Program team.

---

 Centers for Medicare & Medicaid Services. Readmissions Reduction Program. 2014. Available at: <http://www.cms.gov/Medicare/Medicare-Fee-for-Service-Payment/AcuteInpatientPPS/Readmissions-Reduction-Program.html>. Accessed January 14, 2015.

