## PURPOSE & HYPOTHESIS

Our central hypotheses are that handheld spirometry is feasible for inpatient and at-home use and is equally efficacious at determining lung function when compared with bedside spirometry measurements. To test these hypotheses, we propose the following specific aims:

**Specific Aim 1:** Determine the correlation of SpiroPD handheld spirometry measurements with bedside Koko spirometry lung function.

**Hypothesis:** Correlation between the two lung function tests will be substantial for both hospitalized and ambulatory patients.

**Specific Aim 2:** To determine the feasibility, adherence, and preliminary management efficacy of home SpiroPD testing.

**Hypotheses:** (1) Patients will demonstrate substantial adherence to daily home spirometry testing; (2) medication adherence will increase significantly in patients who are adherent to daily home spirometry testing; (3) acute care utilization will decrease significantly in adherent patients.

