## METHODS OVERVIEW

We will enroll patients diagnosed with COPD both in the hospital and clinic setting and follow for 30 days. Participants will complete comparative lung function measurements with both devices while in the hospital or clinic at time of enrollment and at the 30-day follow up visit. Correlation will be assessed using Spearman's correlation coefficient. A high correlation ( $> 0.8$ ) will demonstrate the usefulness of the SpiroPD device in these patients in both settings. We will use the FDA-cleared (K 103575) SpiroPD device for its intended use.

At the time of their initial study visit, study participants will be given a SpiroPD device for use at home following instruction in the hospital or clinic. Patient adherence to daily testing over one-month will be monitored using real-time capture Wi-Fi-data from the SpiroPD data portal. Participant surveys will ascertain barriers and facilitators of daily spirometry lung function testing, and subject attitudes and beliefs about the usefulness of this testing for self-management. Adherence to medication use and utilization outcomes will be measured using patient logs. Acute care utilization will be measured via tracking of ED visits, hospitalizations, and urgent care calls. Information will be collected at the 30 day (+/- 1 week) visit through in-person (preferred) or phone call visits (if do not show for in person visit).

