## **TYPE AND NUMBER OF EXPERIMENTAL SUBJECTS**

We will enroll 150 study participants.

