### **Exclusion Criteria**

1. Currently in an intensive care unit
2. Physician declines to provide consent
3. Patient unable to provide consent (e.g., history of cognitive impairment, unable to understand English) or declines to provide consent

For our study regarding correlation of the Koko with the SpiroPD devices to measure lung function, we will have power to detect a small to moderate effect size ( $p=0.023$ ) at  $>80\%$  ( $87\%$ ) power with  $n=150$  participants at an alpha  $<0.05$ .

Statistical Test (Spearman)	Sample Size	Power	Correlation	Significance Level
Correlation	193.78	0.8	0.2	0.05
Correlation	145.92	0.8	0.23	0.05
Correlation	123.13	0.8	0.25	0.05
Correlation	84.75	0.8	0.3	0.05

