## STATISTICAL ANALYSES

**SA1:** Correlation between KoKo and SpiroPD measurements will be assessed using Spearman's correlation coefficient. A high correlation ( $> 0.8$ ) will demonstrate the usefulness of the SpiroPD device in these patients.

**SA2:** Feasibility process measures such as proportion of participants who adhere to the at-home use of SpiroPD lung function testing, adherence measures to treatment regimens, and estimates of efficacy as denoted by exacerbations and acute care utilization will be analyzed using descriptive statistics. Patient characteristic associated with increased SpiroPD use, treatment adherence, and efficacy of lung function testing will use McNemars, Fishers exact or Chi square testing for categorical variables and rank sum or t-tests for continuous variables.

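### The power statement for n = 150 matches a test of zero correlation at 0.2 to 0.3, not the > 0.8 benchmark that decides Aim 1, and its effect size and 87% power do not pair

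*Combined protocol and SAP*

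**What the plan says.** - **Success benchmark.** STATISTICAL ANALYSES, SA1, uses Spearman's coefficient for KoKo against SpiroPD and states: "A high correlation ( $> 0.8$ ) will demonstrate the usefulness of the SpiroPD device in these patients". METHODS OVERVIEW extends the claim across settings: "A high correlation ( $> 0.8$ ) will demonstrate the usefulness of the SpiroPD device in these patients in both settings".
- **Hypothesis.** Specific Aim 1 under PURPOSE & HYPOTHESIS reads: "Correlation between the two lung function tests will be substantial for both hospitalized and ambulatory patients".
- **Sample size.** "We will enroll 150 study participants". No split between inpatients and outpatients is given.
- **Power.** After the exclusion criteria the plan says "we will have power to detect a small to moderate effect size ( $p=0.023$ ) at" more than 80% (87%) power, with n = 150 and alpha below 0.05. The table beneath is labelled as Spearman. It lists sample sizes of 193.78, 145.92, 123.13 and 84.75 for correlations of 0.2, 0.23, 0.25 and 0.3, all at power 0.8 and significance level 0.05. Neither the null hypothesis nor the number of sides is stated.
- **Data.** METHODS OVERVIEW plans "comparative lung function measurements with both devices while in the hospital or clinic at time of enrollment and at the 30-day follow up visit", so there are two possible pairs per participant. SA1 does not say which visit is analysed.

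**The concern.** A power statement should concern the question the analysis will answer. Aim 1 asks whether the correlation exceeds 0.8, but the table stops at 0.3. If the calculation is a test against zero, it is significant at n = 150 for any observed correlation above about 0.16. Two spirometers measuring the same lungs should clear that easily, so the stated power says nothing about reaching 0.8.

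Readers who take the 87% as the strength of Aim 1 would be misled, and they would not learn how uncertain an estimate close to 0.8 is. That matters because the plan says that demonstrating usefulness "will set the stage for appropriate next-step studies and NIH grant applications". The mismatch between the sentence and its table also makes it unclear which effect size the sample size was meant to serve.

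**Working it through.** **Inputs.** From the documents: n = 150, alpha 0.05, the four table rows, the printed effect size 0.023, the printed power 87% and the benchmark 0.8. Assumed: one evaluable KoKo-SpiroPD pair per participant, at enrolment.

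**1. Reproduce the table.** Two-sided test of rho = 0 by Fisher's z:

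N = ((1.960 + 0.842) / atanh(r))² + 3

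For r = 0.23, atanh(0.23) = 0.2342, which gives N = 146.11.

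| r | Table | Two-sided | One-sided |
|---|---|---|---|
| 0.20 | 193.78 | 193.97 | 153.4 |
| 0.23 | 145.92 | 146.11 | 115.7 |
| 0.25 | 123.13 | 123.32 | 97.8 |
| 0.30 | 84.75 | 84.93 | 67.5 |

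The two-sided column agrees within 0.2 participants in every row; the one-sided column does not. The null of zero is inferred from this match.

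**2. Check the power sentence.** Power at n = 150 is Φ(atanh(r) × √147 − 1.960), with √147 = 12.124. At 0.023 the small opposite tail is added.

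- r = 0.23: Φ(2.839 − 1.960) = 81%.
- r = 0.25: Φ(3.097 − 1.960) = 87%.
- r = 0.023, taken literally: about 6%.
- One-sided at r = 0.23: Φ(2.839 − 1.645) = 88%, or 87% with the Spearman variance factor 1.06. This comes close to the sentence but contradicts the two-sided table.
- Two-sided power of 87% at r = 0.23 would need about 176 participants.

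**3. Precision at the benchmark.** 95% interval: tanh(atanh(0.80) ± 1.960 × √(c/(n − 3))), with atanh(0.80) = 1.0986. Three choices of c for the variance:

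| n | c = 1 | c = 1.06 | c = 1 + r²/2 = 1.32 |
|---|---|---|---|
| 150 | 0.734 to 0.851 | 0.732 to 0.852 | 0.723 to 0.858 |

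In simulation at a true Spearman correlation of 0.80 and n = 150, coverage was 92.9%, 93.7% and 96.2% respectively. The last formula is therefore the cautious choice, and it gives 0.72 to 0.86. With an assumed 120 evaluable pairs it gives 0.71 to 0.86.

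By setting, at an assumed 75 each, the lower limit is 0.68 to 0.70 and the upper limit 0.87 to 0.88 across formulas.

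**4. How the > 0.8 rule behaves at n = 150.** From 20,000 simulated bivariate-normal samples per true value:

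| True Spearman correlation | Chance that the estimate exceeds 0.8 |
|---|---|
| 0.70 | 0.4% |
| 0.75 | 7.6% |
| 0.80 | 48% |
| 0.85 | 95% |

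**The case against.** **It is a pilot, and 0.8 can be read as a descriptive cut-off on the point estimate.** That is a fair reading, since no hypothesis test of 0.8 is stated. On that reading 150 participants serve well, and an interval could be added at analysis. This limits the consequence. It does not rescue the power statement, because the plan says a value above 0.8 will demonstrate usefulness and supports its sample size with a calculation about something else.

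**A reader might infer that the trial is underpowered.** The documents do not support this. For the 95% lower limit to exceed 0.8, the observed correlation would have to be about 0.85 to 0.86, but the plan sets no lower-limit rule. Under the rule it does set, 150 participants separate clearly poor from clearly good agreement in ranking.

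**A reader might infer that the 87% has no source in the table, or that true power is about 6%.** Neither follows. At n = 150, 87% fits the table's 0.25 row. The 6% depends on taking 0.023 literally beside a table that lists 0.23, and a misprint is far more likely. What stands is narrower: under the table's two-sided test, 87% goes with neither 0.023 nor 0.23.

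**A reader might infer that the plan ignores the two settings.** Aim 1 and METHODS OVERVIEW already imply results for each, and SA1 may simply be brief. This is a secondary point about making the analysis text explicit. The per-setting intervals also rest on an assumed split.

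**Conclusion.** The point holds as a mismatch between the stated justification and the benchmark, together with an inconsistency inside the power sentence. The table matches a two-sided test of zero correlation at 0.2 to 0.3, whereas Aim 1 is judged at 0.8, for which the plan states no power, interval or precision. The sentence should pair 0.23 with 81% or 0.25 with 87%.

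The consequence is moderate. Enrolment, data collection and the estimator are unaffected. What the reader lacks is that an observed 0.80 is compatible with values down to 0.72 or 0.73 overall, and down to 0.68 to 0.70 in one setting if the settings had 75 each.

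These figures assume one evaluable pair per participant, and the pass rates assume bivariate-normal data. The zero null rests on the numerical match, which is close in all four rows. It should be corrected before the plan is relied on, but it does not put the study in doubt.

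**What to change.** Replace the power paragraph and table with a precision statement that names the visit, for example:

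> With 150 evaluable KoKo-SpiroPD pairs (one per participant, at enrolment), an observed Spearman correlation of 0.80 has a 95% CI of about 0.72 to 0.86.

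Add the matching interval for the number expected in each setting once a split is anticipated.

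In SA1, state that the correlation will be reported with its 95% interval, overall and separately for inpatients and outpatients, and that the 0.8 benchmark will be interpreted alongside the interval.

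If the existing power text is kept as background, label it a two-sided test of rho = 0 and make its figures agree (0.23 with 81%, or 0.25 with 87%). Do not change enrolment.

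The cost is rewording one paragraph and SA1, with no added participants, visits or data. The downside is presentational. The design figure will look less favourable than 87% power, estimates near 0.8 will be shown with their uncertainty, and the wider per-setting intervals may make a setting with an estimate above 0.8 look less conclusive.

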## **DURATION**

Participants will be asked to use the SpiroPD device for 30 days after discharge from the hospital or starting the day after the clinic visit if recruited from clinic. They will be in the study for 30 days (with a window of +/- 1 week for the 30 day visit) from the time of enrollment.

Electronic data will be collected from the time of electronic medical record initiation at University of Chicago (11/1/2008) until 90 days past the day of enrollment.

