## **DATA SHARING**

A summary final report will be provided to the SpiroPD manufacturer. Individual level data will not be provided. The final report should include de-identified summary data for those receiving a SpiroPD device:

- Used SpiroPD Y/N
- If Y—usage data (# of uses)
- If Y—lung function data from SpiroPD
- If Y-- Medication adherence from SpiroPD
- Gender
- Age
- Pre/post study health care utilization
- Insurance type
- Demographics

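### SA2 fixes no cut for adherent SpiroPD use and names only group or paired tests, although a 30-day use count is captured; a graded measure would be better and costs little

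*Combined protocol and SAP*

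**What the plan says.** The Statistical Analyses section (SA2) lists as a feasibility measure the "proportion of participants who adhere to the at-home use of SpiroPD lung function testing", which is a yes/no class per participant. It says that this measure, treatment adherence and utilization "will be analyzed using descriptive statistics". A second sentence on patient characteristics names McNemar, Fisher exact, chi-square, rank sum and t-tests.

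Purpose & Hypothesis (Specific Aim 2) states three hypotheses:

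- The first concerns home testing itself: "Patients will demonstrate substantial adherence to daily home spirometry testing".
- The second predicts a significant rise in medication adherence among those who keep to the daily tests.
- The third concerns utilization: "acute care utilization will decrease significantly in adherent patients".

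The underlying data are finer than a yes/no class. Methods Overview: "Patient adherence to daily testing over one-month will be monitored using real-time capture Wi-Fi-data from the SpiroPD data portal". Duration: "Participants will be asked to use the SpiroPD device for 30 days after discharge". Data Sharing lists "usage data (# of uses" as a reportable item. No section gives the number of days, sessions or percentage that makes a participant adherent, what level counts as substantial, or when either is fixed.

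**The concern.** The same undefined class does three jobs. It is the descriptive result for hypothesis (1), and it defines the patients in whom hypotheses (2) and (3) predict significant change. Device Data Collection makes the readings available to the research team, and the Data Safety Monitoring Plan has monthly data reports, so usage will be known as it accrues. Nothing in the plan prevents the boundary from being drawn after usage, and possibly outcomes, have been seen.

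Two things are at stake. If several boundaries are tried, the false-positive rate for a link between home testing and medication adherence or acute care exceeds 5%. If the true relation is graded, splitting a 30-day count into two classes loses power. The Background says that the pilot is meant to lead to next-step studies and grant applications, so a chance association could be carried forward.

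**Working it through.** **Inputs.** From the documents: n=150 (Type and Number of Experimental Subjects), a 30-day period of use (Duration), and a 0.05 level (sample-size paragraph and table under Exclusion Criteria). Assumed: a use–outcome correlation r of 0.23, with 0.30 as a second value. Both appear in the sample-size table, but that table concerns KoKo–SpiroPD agreement (SA1). The plan gives no figure for SA2.

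**1. Check of the formula on the plan's own table.** Two-sided Fisher z: n = ((1.960 + 0.842)/atanh(r))² + 3. For r=0.23 this gives 146.11, against 145.92 in the table. The other rows give 193.97, 123.32 and 84.93, against 193.78, 123.13 and 84.75. The formula therefore reproduces the table to within 0.2.

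**2. Power with graded use.** Power = Φ(atanh(r)·√(n−3) − 1.960). With r=0.23 and n=150: 0.2342 × 12.124 = 2.839, and Φ(0.879) = 0.81. With r=0.30 the result is 0.96.

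**3. Power after a split (normal model).** Dichotomising a normal predictor with share p adherent multiplies r by φ(c)/√(p(1−p)), where c is the normal quantile at p. The reduced r goes into the same formula. The last column is the n needed for 80% power at r=0.23; graded use needs about 147.

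| Share adherent | Factor | Reduced r (from 0.23) | Power, r=0.23 | Power, r=0.30 | n for 80% power |
|---|---|---|---|---|---|
| 50% | 0.798 | 0.184 | 61% | 84% | 231 |
| 70% | 0.759 | 0.175 | 57% | 80% | 256 |
| 80% | 0.700 | 0.161 | 50% | 73% | 301 |
| 90% | 0.585 | 0.135 | 37% | 57% | 432 |

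**4. Power after a split (count model).** Simulation: days used ~ binomial(30, π), π ~ Beta(1.5, 1.2), a linear effect with r=0.23, a normal outcome, and a t-test at the cut against a Pearson test on the count. Power is about 82–83% graded. It is about 68–69% at a 60% cut, 53–54% at 80% and 36% at 90%. The Beta distribution is an assumption and makes only about 25% of patients adherent at an 80% cut. Under a higher-use Beta(4, 1.2), power at the 80% cut is about 65%, still below graded use.

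**5. Cut chosen after the fact.** Null simulation, n=150, smallest p-value over the candidate cuts:

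- one cut fixed in advance: about 5%
- best of three (15, 21, 24 days): about 11%
- best of five (15 to 27 days): about 16%
- best of six (50% to 90% of days): about 16–20%, depending on the usage distribution

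If adherent status is instead a filter, and change is tested within the selected patients, the best of six gives about 13% under the higher-use distribution and about 15% under the lower-use one.

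**6. Where a split wins.** If the true effect is a step at 80% of days (r=0.23 with the split, lower-use distribution), power is about 82% for that split and about 53% for the continuous test.

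**The case against.** The strongest reply is that SA2 is a descriptive plan for a pilot. The sentence containing the adherence proportion announces descriptive statistics, and SA2 assigns no explicit test to the effect of home testing on medication adherence or acute care. This stands, and it limits the importance of the point. It does not remove it: Specific Aim 2 twice predicts significant change in the adherent class, and even the descriptive proportion cannot be computed without a cut.

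A reader might also infer several stronger things that the documents do not support.

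- *That the plan commits to comparing adherent with non-adherent patients.* Hypotheses (2) and (3) can equally be read as change within adherent patients. Utilization is collected before enrollment and during the study, Data Sharing lists it pre and post, and McNemar is a paired test. On that reading the power figures in steps 3 and 4 do not describe the analysis, but the open cut then selects the analysis set and step 5 still applies.
- *That 0.23 is the plan's effect size for this question.* It is an SA1 device-agreement figure, used here only to show scale.
- *That graded analysis is ruled out.* SA2's reference to increased SpiroPD use leaves room for it, but the term is undefined and no listed test relates days used to an outcome.
- *That a graded analysis always has more power.* Step 6 shows the exception. The simulations also assume a normal outcome, whereas 30-day acute care use is a count.

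**Conclusion.** The point holds as a cheap improvement. The plan uses adherent as a yes/no class without a cut, predicts significant change in that class, and names only group or paired tests, while a better measure is already captured. If the effect is monotone with r=0.23, n=150 and a two-sided 0.05 level, power is about 81–83% with graded use and about 36–69% after a split, depending on the cut and the usage distribution. An after-the-fact choice among six cuts takes type I error from 5% to about 16–20%, or about 13–15% for within-subgroup change. The power loss rests on an assumed effect size, an assumed usage distribution and a graded effect. The inflation rests only on several cuts being tried.

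Nothing in the documents suggests that anyone intends to choose the cut from the data; the plan simply does not exclude it. Nor would a graded exposure make the association causal, since patients who test daily may differ in other ways that affect the outcomes.

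**What to change.** Change the SA2 wording as follows.

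- Make the percent of available home days with a recorded session the adherence measure, and report its median, IQR and distribution. Define a recorded session and an available day. Duration counts use from discharge but study participation from enrollment, so the denominator for inpatients must be stated. Days in hospital should not count as missed tests, or acute care use would itself lower adherence.
- For hypotheses (2) and (3), relate this percentage as a graded exposure to change in medication adherence and to pre/post acute care use, by rank correlation or by regression suited to counts.
- Keep one cut, fixed before outcome data are reviewed, for the descriptive proportion with its 95% CI.
- Label the results for hypotheses (2) and (3) as exploratory associations.

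The cost is wording only, because the data are already captured. A slope or rank correlation is slightly harder to present than two groups, and it is less sensitive to a pure threshold effect.

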### Survey Data Collection

Trained research staff will assess the following at the initial enrollment, post-discharge follow-up visit (for hospitalized patients), and at the 30-day follow-up:

- Demographics
- Self-reported health care utilization
- respiratory symptoms/morbidity
  - o Modified Borg Dyspnea Scale
  - o Modified Medical Research Council (MMRC) Dyspnea Scale
  - o COPD Assessment Tool
- Self-reported medication adherence
  - o MARS
- Quality of Life
  - o St. George's Respiratory Questionnaire-COPD
- Health Literacy: Ask brief health literacy screen questions for all participants
  - Brief Health Literacy Screen (BHLS) – three questions
    - o How often do you have problems learning about your medical condition because of difficulty understanding written information?
    - o How confident are you filling out medical forms by yourself?

- How often do you have someone help you read hospital material?
- SpiroPD use
  - SpiroPD Pre-Education Survey
  - SpiroPD Post-Education Survey
  - SpiroPD Follow-Up Survey
  -
- Assess vision with Snellen Chart
  - Chart should be two chart lengths away from participant
  - Ask participant to cover their right eye and use their left eye to read the smallest line they can from the chart
  - Ask participant to cover their left eye and read the smallest line they can with their right eye
  - Administrator should follow patient's reading on a copy of the chart included in forms
  - Record acuity in right and left eyes
  - If vision is not better than 20/40 in at least one eye attempt to correct vision with non-prescription glasses
    - 4 strengths of glasses: 2.00, 2.25, 2.75, and 3.25
    - Start with 2.00, and repeat the vision screen, with each eye separately
    - If visual acuity of 20/40 is reached in at least one eye, the patient is eligible to complete the STOHFLA HL evaluation using the readers
  - If vision is not corrected after trying all of the strengths of the readers, the patient is ineligible to complete the STOHFLA HL evaluation

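### Aim 2 hypotheses (2) and (3) predict significant changes in adherent patients, but SA2 only describes these outcomes: it specifies no test of change, no analysis against SpiroPD use, and no role for the baseline data collected

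*Combined protocol and SAP*

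**What the plan says.** Under Purpose & Hypothesis, Aim 2 is "To determine the feasibility, adherence, and preliminary management efficacy of home SpiroPD testing". Hypothesis (2) is that "medication adherence will increase significantly in patients who are adherent to daily home spirometry testing". Hypothesis (3) is that "acute care utilization will decrease significantly in adherent patients".

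Under Statistical Analyses, the first SA2 sentence covers feasibility measures, treatment-adherence measures and efficacy estimates (exacerbations and acute care use), and says that all of these "will be analyzed using descriptive statistics". The second sentence concerns "Patient characteristic associated with increased SpiroPD use, treatment adherence, and efficacy of lung function testing", which "will use McNemars, Fishers exact or Chi square testing for categorical variables and rank sum or t-tests for continuous variables".

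Baseline information is planned in several places:
- Survey Data Collection begins "Trained research staff will assess the following at the initial enrollment" and goes on to a post-discharge visit (inpatients) and the 30-day follow-up. The list includes MARS and self-reported utilization.
- The Study Schema marks self-reported utilization at baseline and at 30 days.
- Medical Record and Administrative Data Collection takes ED visits, hospitalizations, outpatient visits and observation stays for the 12 months before enrolment and for the study period. Records run to 90 days after enrolment.
- Data Sharing lists pre/post utilization for the report to the manufacturer.

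**The concern.** Both hypotheses predict a change, in a stated direction, in a subgroup defined by device use, and call it significant. A descriptive summary can show the direction of a difference but cannot support a claim of significance. Nor does SA2 say which contrast is meant: before against after within adherent patients, or adherent against non-adherent patients.

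Interpretation is at stake. All participants receive the device, so there is no control group, and patients choose how much they use it. Those who test daily may well have taken their medication more reliably and used less acute care from the start. Inpatients are enrolled during an admission, so lower use afterwards is plausible without any device effect. A falling count or a better 30-day score in adherent patients could then be read as efficacy, and nothing in SA2 guards against that.

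**Working it through.** **1. Hypotheses against analyses.**

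| Element needed | Hypothesis (2), medication adherence | Hypothesis (3), acute care use |
|---|---|---|
| Named method in SA2 | descriptive | descriptive |
| Test of change | none | none |
| Analysis against SpiroPD use | none | none |
| Cut-off defining an adherent patient | none | none |
| Baseline collected | yes (MARS at enrolment) | yes (self-report; 12-month records) |
| Role for baseline in SA2 | none stated | none stated |
| Power or precision | none | none |

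The only power statement, placed after the Exclusion Criteria, concerns the KoKo–SpiroPD correlation, so there is no planned figure to reproduce for these hypotheses.

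**2. Does the second SA2 sentence fill the gap?** It looks for patient characteristics associated with three things: device use, treatment adherence and efficacy. Device use stands there as an outcome beside the other two, not as the exposure. McNemar's test is paired, but it needs a binary before-and-after outcome and none is named. The rank sum test is unpaired, and the t-tests are not said to be paired.

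**3. Unequal windows for utilization.** Inputs: a 12-month prior window, 30 days of participation (Duration) and records to 90 days. With a constant event rate and no device effect:
- 30-day count / 12-month count = 30/365 = 0.082, an apparent fall of 1 − 0.082 = 92%.
- 90-day count / 12-month count = 90/365 = 0.247, an apparent fall of 1 − 0.247 = 75%.

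No conversion to a common rate is stated.

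**4. What 150 patients could show (illustration only).** Assumptions: two-sided 0.05, 80% power, no loss to follow-up, and 50% to 80% of patients adherent. The documents give no adherent share. The multiplier is 1.960 + 0.842 = 2.802.
- Change within adherent patients, in SDs of the change: 2.802/√75 = 0.32; 2.802/√120 = 0.26.
- Adherent against non-adherent, in SDs: 2.802 × √(1/75 + 1/75) = 0.46; 2.802 × √(1/120 + 1/30) = 0.57.
- Acute care, if 30% of non-adherent patients have an event (assumed): the detectable proportion in adherent patients is 11.6% to 9.1%. If 20% (assumed): 5.0% to 3.6%. The relative reductions run from (30 − 11.6)/30 = 61% to (20 − 3.6)/20 = 82%.

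Under these assumptions a moderate MARS difference is within reach, but only a very large difference in acute care use would be detected.

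**The case against.** The strongest defence is that this is a single-center pilot. Aim 2 calls efficacy preliminary, SA2 speaks of estimates, and the Data Safety Monitoring Plan calls the study observational. Descriptive analysis suits that purpose. This stands, and it is a good reason to soften the hypotheses. It does not justify pairing predictions of significance with an analysis that cannot deliver them.

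A reader might infer something stronger: that no baseline values exist, or that the study is unable to test these hypotheses. The documents support neither. Baseline MARS and prior utilization are collected, and the data would permit a paired or between-group comparison. SA2 also names inferential tests touching treatment adherence and efficacy, although it aims them at patient characteristics. The gap is in what SA2 specifies.

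It is also fair to object that a regression on device use has its own weakness. For acute care, use and events over the same 30 days invite reverse causation: a readmitted patient may be unable to test at home, so the event lowers measured use. A person-time offset and adjustment for prior events do not cure this, so the timing of exposure must be dealt with explicitly. Finally, a regression across all patients estimates an association with level of use, not change within an adherent subgroup, so the hypotheses need rewording to match.

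**Conclusion.** The point holds as a mismatch between hypotheses and analysis. For two of the three Aim 2 hypotheses, SA2 names a method that cannot support the stated conclusion, relates neither outcome to SpiroPD use, and leaves the collected baseline data without a role. This should be corrected before analysis.

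The size that can be stated concerns utilization: comparing unconverted counts would build in an apparent fall of 92% (30 days) or 75% (90 days), assuming a constant event rate. This describes a risk that the plan leaves open; the documents do not say that raw counts will be compared. The size of any confounding by self-selected use cannot be derived from the documents. The detectable effects rest on assumed adherent shares and event proportions and serve only to show why hypothesis (3) in particular should be exploratory.

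**What to change.** In SA2, replace the descriptive treatment of these two outcomes as follows:

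- **Hypothesis (2).** Linear regression of the 30-day MARS score on percent of days SpiroPD was used, adjusted for baseline MARS and enrolment setting (inpatient or clinic). Report the estimate with a 95% CI as an association. Percent of days as a continuous exposure avoids the undefined adherence cut-off; define its denominator. Add a MARS row to the Study Schema so that it agrees with Survey Data Collection.
- **Hypothesis (3).** Acute care events as rates per person-time (negative binomial, or Poisson with robust errors, with a log person-time offset), adjusted for the prior-12-month rate and setting. Measure device use before the events that are counted, for example early use against later events, or over days at home only. Report with a 95% CI as exploratory.
- **Purpose & Hypothesis.** Reword (2) and (3) as exploratory associations with level of device use and drop the claim of significance, in line with the preliminary framing of Aim 2.
- **Utilization summaries.** Present any pre/post figures, including those for the manufacturer, as rates on a common time base.

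The cost is a text amendment and two standard regressions on data already planned. The efficacy language becomes more modest, residual confounding remains, and the early-window option discards some events.
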